3.3.1 Adrenal insufficiency (AI) status

Adrenal insufficiency will be diagnosed by the following method: for patients who have reached OCS doses equal to 5 mg/day, HPA axis integrity will be assessed at the end of a 4-week period on 5 mg/day by evaluating the morning cortisol levels (8-9 am). For those patients who had baseline OCS doses equal to 5 mg/day, HPA axis integrity will be assessed 4 weeks after the first dose of benralizumab administration and before initiation of the OCS reduction phase. The process will be as described in Figure 2.

Figure 2 HPA axis evaluation

Details related to values for normal, indeterminate/partial AI, and complete AI are provided in the laboratory manual and copied here for ease of reference:

Morning Cortisol Test:

Normal: >350 nmol/L; Indeterminate AI: 100-350 nmol/L; Complete AI: <100 nmol/L

ACTH Stimulation Test:

Normal: >450 nmol/L; Partial AI: 250-450 nmol/L; Complete AI: <250 nmol/L

For patients taking oral oestrogen containing contraceptives, morning cortisol test ranges will be 2X the above ranges, and ACTH stimulation test ranges will be 1.5X the above ranges.

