## **5.2 Safety assessments**

### **5.2.1 HPA axis evaluation**

For all patients, HPA axis integrity will be evaluated after 4-weeks on 5 mg/day and prior to tapering down the OCS dose (for patients with baseline OCS doses equal to 5 mg/day, this will be assessed 4 weeks after the first dose of benralizumab administration and before initiation of the OCS reduction phase)

First, a screening method with morning serum cortisol is done (8-9 am morning cortisol level), to evaluate whether the patient has:

- Normal cortisol levels
- Complete adrenal insufficiency (AI)

Cortisol levels from the morning cortisol test that are below normal range and above the Complete AI range are considered “Indeterminate,” and require additional testing described below.

Secondly, the ACTH stimulation test (ie, Synacthen®, Cortrosyn™) is done within approximately 1 week in the subset of patients with indeterminate results from the morning cortisol test [see also Section [5.2.1.2](#) for details]. The ACTH stimulation test is more specific than the morning cortisol test, and can determine whether the patient has:

[figure not shown]
- Normal cortisol levels
- Complete AI
- Partial AI.

The process will be as described in [Figure 2](#).

For females using oral estrogen-containing contraceptives or oral estrogen-containing hormone replacement therapy, the threshold for normal values will be 2 times the normal morning cortisol levels and 1.5 times the normal ACTH stimulation test cortisol levels. Details related to values for normal, partial AI, and complete AI for these patients are provided in the laboratory manual.

For the morning cortisol test, the last OCS dose should be taken  $\geq$  24 hours prior to testing. Additionally, patients must not take ICS (or ICS/LABA if in single inhaler) treatment on the morning of the cortisol testing (for patients taking a once-daily ICS/LABA formulation, e.g. fluticasone furoate/vilanterol patients must not take the treatment  $\leq$  24 hours prior to the morning of the cortisol testing). If a patient requires a short course of macrolides, antivirals, or azoles, there must be a window of  $\geq$ 1 week prior to the testing of cortisol levels (see Section [7.8](#)).

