**Figure 2 HPA axis evaluation**

**Figure 2:** For normal cortisol levels with concurrent signs/symptoms of AI, OCS down-titration should continue at a slower pace (1 mg Q4W). For complete AI identified via morning cortisol testing, refer to section 5.2.1.1 for instructions on 3-month repeat testing. For partial AI or complete AI identified via ACTH stimulation test see Section 5.2.1.2 for instructions on 2-month or 3-month repeat testing respectively. Patients who have Partial AI will undergo an additional morning cortisol test (and if required, ACTH stimulation test for indeterminate result) approximately 1-2 weeks prior to the end of the OCS Reduction phase. Patients who have Complete AI or Partial AI at the end of the OCS Reduction Phase, will undergo a final morning cortisol test (and if required, ACTH stimulation test for indeterminate result) approximately 1-2 weeks prior to the end of the Maintenance phase (prior to EOT).

*Note:* Central lab reports list reference ranges that are different than this study-reference ranges. To interpret laboratory results for each morning cortisol or ACTH stimulation test, please look for the study-specific lab alerts indicating normal, partial AI, and complete AI on the lab reports provided by central labs. The study-specific reference ranges for normal, partial AI, and complete AI are provided in the laboratory manual.

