4.2.7.1 AI status

The number and percentage of patients with complete or indeterminate AI at the morning cortisol test will be tabulated along with the number and percentage with a result in the normal range. For those showing complete or partial/indeterminate AI, results of the subsequent ACTH stimulation tests and/or further morning cortisol tests will be tabulated so that pathways through the AI testing schematic can be evaluated. At DBL1, morning cortisol test and ACTH stimulation test results are presented for the initial morning cortisol test and repeat morning cortisol test; at DBL2, the additional tests at the end of OCS reduction phase and end of maintenance phase if applicable will also be summarised. Patients AI status (normal/partial AI/complete AI) at each stage will also be tabulated. Results will be repeated by baseline OCS dose and baseline duration of chronic OCS use.

A shift table will be presented for patients from their initial morning cortisol test to final AI status at the end of OCS reduction phase. A similar shift table will be presented for patients from their initial morning cortisol test to their final AI pathway status, including test results up to the end of the maintenance phase. Two additional shift tables will be presented which will include all available data at or after the protocol-defined initial morning cortisol test regardless of AI pathway compliance: the first showing AI status at the initial morning cortisol test vs. AI status at the additional test at the end of the maintenance phase; and the second showing AI status at the initial morning cortisol test vs. final AI status recorded ever in the study.

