In addition, spaghetti plots will be produced for patients with partial AI (as determined by the ACTH stimulation test) following both the initial and repeat morning cortisol tests. The plots will show all available cortisol levels from the initial morning cortisol test, the repeat morning cortisol test and the end of the OCS reduction phase (if applicable). Morning cortisol test results and ACTH stimulation test results will be plotted side by side. Patients receiving oral oestrogen containing contraceptives will be plotted on separate pages. Similar plots for patients with partial AI at the initial morning cortisol test (ACTH stimulation test) and complete AI at the repeat morning cortisol test (\pm ACTH stimulation test) will also be produced. At DBL2, these graphic presentations will be repeated including all available cortisol data from the initial morning cortisol test, the repeat morning cortisol test, the end of the OCS reduction phase and the end of maintenance phase.

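### SAP 3.3.1 and 4.2.7.1 recognise only oral contraceptive users for the oestrogen-adjusted cortisol ranges, whereas protocol 5.2.1 also covers women on oral oestrogen HRT

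*SAP*

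**What the plan says.** Protocol 5.2.1 defines who gets adjusted cortisol limits: "For females using oral estrogen-containing contraceptives or oral estrogen-containing hormone replacement therapy, the threshold for normal values will be 2 times" the usual morning level, and 1.5 times the usual level for the ACTH stimulation test. For the full set of limits it points elsewhere: "Details related to values for normal, partial AI, and complete AI for these patients are provided in the laboratory manual". The note to protocol Figure 2 warns sites that the reference ranges on central laboratory reports are not the study's ranges. It tells them instead: "please look for the study-specific lab alerts indicating normal, partial AI, and complete AI on the lab reports provided by central labs".

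SAP 3.3.1 prints numeric limits and says that they "are provided in the laboratory manual and copied here for ease of reference". Morning cortisol is Normal above 350, Indeterminate from 100 to 350 and Complete AI below 100 nmol/L. After ACTH it is Normal above 450, Partial AI from 250 to 450 and Complete AI below 250 nmol/L. The adjustment follows: "For patients taking oral oestrogen containing contraceptives, morning cortisol test ranges will be 2X the above ranges". For these same patients the second test has a parallel rule with a multiplier of 1.5, again applied to the ranges as a whole. HRT is not mentioned.

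SAP 4.2.7.1 uses the same narrower group for the cortisol plots: "Patients receiving oral oestrogen containing contraceptives will be plotted on separate pages". SAP 1.2 also prints the 250 to 450 nmol/L Partial AI range, with no oestrogen adjustment. SAP section 6 lists three changes from the protocol, and this is not among them.

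**The concern.** The two documents define the adjusted group differently. A programmer who follows SAP 3.3.1 will apply the unadjusted limits to an oral-HRT user. Under protocol 5.2.1 the same woman has a higher threshold for Normal. She can therefore be called Normal in the analysis at a value that the protocol places below normal.

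The classification is used in several places. SAP 4.2.7.1 tabulates AI status at each stage, builds the testing-pathway tables and the shift tables, and selects patients for the plots. SAP 4.1 uses AI status for the subgroups in which change in OCS dose is summarised, and SAP 4.2.5.1 uses it as tabulation subgroups for baseline characteristics. The pathway table is conditional on the morning result: "For those showing complete or partial/indeterminate AI, results of the subsequent ACTH stimulation tests and/or further morning cortisol tests will be tabulated". An HRT user tabulated Normal at the morning test could therefore be left out of that table even though an ACTH test was done. The SAP does not say whether analysis status is taken from the laboratory's study-specific alerts or recomputed from the printed ranges, so nothing in the text rules this out.

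**Working it through.** The plan states no figure on this point that could be reproduced. The check is a comparison of texts followed by multiplication of the printed limits.

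**Inputs.** Base limits: SAP 3.3.1. Multipliers: 2 (morning) and 1.5 (ACTH), the same in SAP 3.3.1 and protocol 5.2.1. Adjusted group: contraceptives only in the SAP, contraceptives or HRT in the protocol (oral oestrogen in both). The protocol prints no base limits, so the check assumes that the SAP values are those of the laboratory manual, as the SAP says.

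**Formula.** Adjusted normal threshold = multiplier × base normal threshold.

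| Test | Limits for an oral-HRT user under the SAP text (nmol/L) | Normal threshold under protocol 5.2.1 | Values classed differently |
|---|---|---|---|
| Morning cortisol | Normal >350; Indeterminate 100–350; Complete AI <100 | 2 × 350 = 700 | >350 to 700: Normal (SAP) against Indeterminate (protocol) |
| ACTH stimulation | Normal >450; Partial AI 250–450; Complete AI <250 | 1.5 × 450 = 675 | >450 to 675: Normal (SAP) against Partial AI (protocol) |

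For example, a morning value of 500 is Normal under the SAP text and Indeterminate under the protocol. A stimulated value of 600 is Normal under the SAP text and Partial AI under the protocol. At 750 (morning) or 700 (ACTH) the two agree.

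**Weight of one patient.** SAP 4.1 takes the whole analysis set as denominator. With the planned 600 patients, each reclassified patient moves a percentage by 100/600 = 0.17 points. The documents do not give the number of women on oral HRT, so no total can be computed.

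**The lower limits, as a query.** SAP 3.3.1 scales the ranges as a whole, so the complete-AI limits for contraceptive users become 2 × 100 = 200 (morning) and 1.5 × 250 = 375 (ACTH). Protocol 5.2.1 states the multipliers for the normal threshold and leaves the other limits to the laboratory manual. The values at stake are 100 to <200 and 250 to <375.

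- If the manual scales only the normal threshold, the SAP calls contraceptive users in these bands Complete AI where the manual would call them Indeterminate or Partial.
- If the manual scales every limit, the SAP is right for contraceptive users, but HRT users in these bands are called Indeterminate or Partial where the manual would call them Complete AI.

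The two cases exclude each other and lead to errors in opposite directions. The manual is not among the documents, so neither is shown.

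**The case against.** The strongest reply is that the SAP only reproduces the laboratory manual for convenience, and that sites acted on study-specific alerts. If analysis status is read from those alerts, the omission in SAP 3.3.1 does no harm. This is possible, but the SAP does not say so. Protocol 5.2.1 also says that the manual gives values for the group that includes HRT users. Either the SAP's copy is incomplete, or manual and protocol differ. Both need reconciling.

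The reply is right on other points:

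- A reader might infer that the SAP contradicts the protocol by scaling the complete-AI limit. The documents do not support this. The protocol never says that the limit is unscaled. It delegates the value to the manual, and the SAP says it copies the manual. The SAP's normal thresholds for contraceptive users (700 and 675) agree with the protocol.
- A reader might infer that the count of patients with complete AI, the key outcome of the AI safety objective, is biased. The documented difference lies wholly above the complete-AI limits. A direct shift at those limits depends on what the manual says, and how a later ACTH result would be handled after a morning value classed Normal is not stated.
- A patient left out of the pathway table would not vanish. SAP 4.2.7.1 adds two shift tables that use all available data regardless of pathway compliance, and SAP 4.1 provides patient-level listings.
- The gap in the plotting rule changes only the page on which a patient's curve appears.

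**Conclusion.** The mismatch in population is real and stands on the text alone: protocol 5.2.1 includes oral-oestrogen HRT users, SAP 3.3.1 and 4.2.7.1 do not, and SAP section 6 is silent. Its size per patient is definite, namely one class less severe at morning values above 350 and up to 700 nmol/L and at stimulated values above 450 and up to 675 nmol/L. Its total size is unknown.

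The misclassification follows only if status is derived from the printed ranges and at least one oral-HRT user has a value in those bands. The outputs are descriptive and no hypothesis is tested on them.

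A reader might also infer an effect on the second primary endpoint, because it depends on AI being the reason for stopping the OCS reduction. The documents do not show one. Under SAP 3.1 the investigator determines and records the final OCS dose, and sites are directed to the laboratory alerts, not to the SAP ranges. Whether the multipliers reach the complete-AI limit is a question for the manual, not a demonstrated discrepancy. Nothing here says which cut-off is clinically right.

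The point is worth correcting because the stated rule, followed literally, classifies identifiable patients differently from the protocol, and the correction is cheap.

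**What to change.** 1. Reconcile SAP 3.3.1, the plotting rule in SAP 4.2.7.1 and the unadjusted Partial AI range in SAP 1.2 with protocol 5.2.1 and the laboratory manual, so that all name the same patient group. Identify women on oral oestrogen-containing HRT at the time of each cortisol test from concomitant medication, assuming the recorded entries show route and composition.
2. State in SAP 3.3.1 whether analysis AI status comes from the study-specific laboratory alerts or from the printed ranges, and list patients for whom the two disagree.
3. Confirm against the laboratory manual that the 2 and 1.5 multipliers apply to the complete-AI limit, as SAP 3.3.1 has it.
4. Record any remaining difference from the protocol in SAP section 6.

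The cost is one or two sentences in 3.3.1, small edits in 1.2 and 4.2.7.1, possibly an entry in section 6, and minor programming. Concomitant medication and cortisol results are already collected. Any AI tables produced at DBL1 need a check for oral-oestrogen users.

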3.3.2 Annualised asthma exacerbation rate

The number of asthma exacerbations and the annualised asthma exacerbation rate will be derived and summarized for the on-study period to end of OCS reduction phase at DBL1, on-study period during maintenance phase, and the overall on-study period at DBL2. On-study period to end of OCS reduction phase is defined as from the day of the first dose of study treatment to the end of OCS reduction phase; on-study period during maintenance phase is defined as from the start of the maintenance phase to the scheduled follow-up visit of the main study; and the overall on-study period is defined as from the day of the first dose of study treatment to the scheduled follow-up visit of the main study. A patient will be considered as having an asthma exacerbation if he/she starts a course of SCS (oral, parenteral) due to asthma, or has an emergency room/urgent care visit or a hospitalisation due to asthma.

The annualised asthma exacerbation rate will be calculated using the time-based approach. Annual asthma exacerbation rate = $365.25 \times \text{total number of exacerbations} / \text{total duration of follow-up (days)}$.

The number and annualised rate of exacerbations requiring hospitalisation or an emergency room visit will also be derived and summarised for the on-study period to end of OCS reduction phase at DBL1, on-study period during maintenance phase, and the overall on-study period at DBL2.

As a sensitivity analysis, annualised exacerbation rates will also be calculated using total duration of follow-up less days with exacerbations (+ 7 days per exacerbation) as the denominator.

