### **5.2.2 Assessment of asthma exacerbations**

During the study, an asthma exacerbation will be defined as a worsening of asthma symptoms that leads to any of the following:

- A temporary bolus/burst of systemic corticosteroids (at a dose above one level higher than the current titration step) for at least 3 consecutive days to treat symptoms of asthma worsening; a single depo-injectable dose of corticosteroids will be considered equivalent to a 3-day bolus/burst of systemic corticosteroids. Note: Per-protocol up-titration of the OCS dose to one level higher is not necessarily considered to be an exacerbation event
  - Patients who experience an exacerbation during the screening period (between Visits 1 and 2) can be granted an extension of the screening period to ensure that a patient recovers from an asthma exacerbation and the OCS dose is stabilized.
- An emergency room or urgent care visit (defined as evaluation and treatment for  $<24$  hours in an emergency department or urgent care center) due to asthma that required systemic corticosteroids (as per the above)
- Inpatient hospitalization (defined as admission to an inpatient facility and/or evaluation and treatment in a healthcare facility for  $\geq 24$  hours) due to asthma

The Investigator must justify the decision for defining an event of worsening asthma as an exacerbation and record it in the source documents and eCRF. An asthma exacerbation that occurs within 7 days of the last dose of systemic steroids, prescribed for a prior exacerbation, will be counted as the same exacerbation event.

The patient may remain in the study after an exacerbation and continue to receive study drug if the Investigator judges that it is medically appropriate for the patient to do so and will be managed as per the details provided in Section [5.2.3](#).

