## **2.3 Assessment and collection of asthma exacerbations:**

Asthma exacerbations will be defined per Section 5.2.2. The Investigator will assess exacerbations at the PONENTE Long Term Follow Up, and if applicable, at any other time when made aware by the patient (Table 8). The Investigator must justify the decision for defining an event of worsening asthma as an exacerbation, and document this justification, including symptoms, in the source documents and the eCRF.

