### **Analysis of safety outcomes**

The number and percentage of patients with complete AI at the Long Term Follow Up visit will be presented for the long term follow up analysis set, biologic analysis set and Benralizumab analysis set. A logistic regression model will be developed to identify factors potentially predictive of long-term adrenal insufficiency. Complete AI status at the Long Term Follow Up visit will be the dichotomous response variable with demographic, respiratory and metabolic baseline characteristics as explanatory variables. Full details will be provided in the SAP.

Spaghetti plots will be produced for patients in the long term follow up analysis set, biologic analysis set and Benralizumab analysis set with partial AI throughout the OCS reduction phase of the main PONENTE study, showing cortisol levels over time until the Long Term Follow Up visit.

The incidence of AEs and SAEs will be summarized over the PONENTE Long Term Follow Up substudy for comparison with incidence rates during the PONENTE main study. Summaries of laboratory parameters and vital signs may be provided, including absolute values and changes over time. Full details will be provided in the SAP.

The annualized rate of asthma exacerbations during the PONENTE Long Term Follow Up substudy will be summarized using mean, 95% CI and dispersion based on the negative binomial distribution, for the long term follow up analysis set, biologic analysis set and Benralizumab analysis set. This will be repeated for exacerbations resulting in hospitalization or an ER visit. Rates will be compared with those recorded during the PONENTE main study. The number and percentage of patients remaining exacerbation-free during the PONENTE Long Term Follow Up substudy will be presented.

Glucocorticoid toxicity index will be summarized over time from the start of the PONENTE main study to the end of the PONENTE Long Term Follow Up substudy, for the long term follow up analysis set, biologic analysis set and Benralizumab analysis set. Statistical correlation between GTI and daily OCS dose will be explored.

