6. CHANGES OF ANALYSIS FROM PROTOCOL

- 1) A sensitivity analysis of the primary outcome has been included in section 4.2.5.2 which excludes any patients with an Important Protocol Deviation related to efficacy. This sensitivity analysis is not specified in the protocol.
- 2) A sensitivity analysis of the first key supportive analysis has been included in section 4.2.5.2 which will require patients with a baseline daily OCS dose of 5mg to achieve a final daily OCS dose of < 5 mg, unless the reason for no further reduction is complete AI. This sensitivity analysis was not included in the protocol.
- 3) In protocol Section 8.5.2.2, a mixed model for repeated measures was planned to analyse the change from baseline in ACQ-6 score. Because phase and study duration will be different between patients, an ANCOVA model will be used to analyse the change from baseline at visit 3, initial morning cortisol test, end of OCS reduction phase and end of maintenance phase, only.

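### SAP 3.3.2 defines an asthma exacerbation more broadly than Protocol 5.2.2, without citing 5.2.2 or declaring the change in SAP section 6

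*SAP*

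**What the plan says.** Protocol 5.2.2 sets the definition for the study. A burst of systemic corticosteroids qualifies if given "at a dose above one level higher than the current titration step) for at least 3 consecutive days"; one depot injection is treated as equivalent. A visit of less than 24 hours qualifies if it was "in an emergency department or urgent care center) due to asthma that required systemic corticosteroids (as per the above". Inpatient hospitalisation for asthma qualifies with no steroid condition. The section adds: "Per-protocol up-titration of the OCS dose to one level higher is not necessarily considered to be an exacerbation event". It also merges events: an exacerbation "within 7 days of the last dose of systemic steroids, prescribed for a prior exacerbation, will be counted as the same exacerbation event". The investigator must justify each exacerbation and record it in the eCRF.

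SAP 3.3.2 gives its own rule: a patient is considered to have an exacerbation if he or she "starts a course of SCS (oral, parenteral) due to asthma, or has an emergency room/urgent care visit or a hospitalisation due to asthma". It does not refer to Protocol 5.2.2. The rate is 365.25 times the total number of exacerbations, divided by total follow-up days. A second rate is restricted to exacerbations requiring hospitalisation or an emergency room visit.

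SAP section 6 lists three departures from the protocol. Two are added sensitivity analyses. The third begins: "In protocol Section 8.5.2.2, a mixed model for repeated measures was planned to analyse the change from baseline in ACQ-6 score". None concerns exacerbations.

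For the long-term follow-up substudy, Protocol Appendix K section 2.3 states: "Asthma exacerbations will be defined per Section 5.2.2". The safety analysis text in Appendix K section 8.5 adds: "Rates will be compared with those recorded during the PONENTE main study".

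**The concern.** The two annualised rates are the key outcome measures for the exacerbation safety objective (Protocol 2.3, SAP 1.1.3), and the event definition is their numerator. One programmer working from the SAP and another working from the protocol could report different rates from the same data. The events on which they would differ are plausible in a steroid-taper study: a burst of one or two days for symptoms, or an emergency visit treated with bronchodilators alone. Such an emergency room visit would enter both rates. If the main-study rate used the broader rule and the substudy rate used 5.2.2, part of any apparent fall during follow-up would come from the definition.

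**Working it through.** No arithmetic in the plan bears on this point, so the first step is to compare the rules.

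| Element | Protocol 5.2.2 | SAP 3.3.2 |
|---|---|---|
| Steroid burst: duration | at least 3 consecutive days, or one depot dose | no minimum |
| Steroid burst: dose | more than one level above the current step | no threshold |
| Emergency or urgent-care visit | must have required qualifying steroids | any such visit due to asthma |
| Hospitalisation for asthma | counts | counts |
| Merging of close events | within 7 days of last steroid dose | not stated |
| Cross-reference to 5.2.2 | – | none |

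The SAP rule therefore drops three conditions and is silent on the merging rule. SAP 3.3.2 does mention 7 days per exacerbation, but as a deduction from follow-up time in a sensitivity analysis. That changes the denominator and does not say how events are counted.

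**Size, as an illustration only.** The documents give no expected exacerbation rate and no frequency for the events in dispute.

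- Patients: 600 (Protocol 8.2).
- Duration: the protocol synopsis gives about 32 to 48 weeks. The lower figure runs to the end-of-treatment visit: for a 5 mg baseline, 4 weeks of induction + 4 weeks from 2.5 mg to 0 mg + 24 weeks of maintenance = 32.
- SAP 3.3.2 counts to the follow-up visit, which is 12 weeks after the last dose. End of treatment is 8 weeks after the last dose, so 12 − 8 = 4 weeks are added, giving 36 to 52 weeks.
- Patient-years = 600 × weeks × 7 / 365.25. At 36 weeks: 151,200 / 365.25 = 414. At 52 weeks: 218,400 / 365.25 = 598. No withdrawals are assumed.
- Each extra counted event adds 1/598 = 0.0017 to 1/414 = 0.0024 per patient-year.
- If 1% to 10% of patients had one extra counted event (assumption), that is 6 to 60 events. Six events add 6/598 = 0.010 to 6/414 = 0.014. Sixty add 60/598 = 0.100 to 60/414 = 0.145.

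In relative terms, if a share q of the events counted under the SAP rule failed 5.2.2, the SAP rate would exceed the 5.2.2 rate by a factor of 1/(1 − q): 1.05 at q = 5%, 1.11 at 10%, 1.25 at 20%, and 1.00 at q = 0. These values of q are also assumptions.

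**The case against.** The strongest reply is that the SAP sentence is a loose paraphrase and the data are 5.2.2 events anyway. Investigators must justify each exacerbation and enter it on a dedicated eCRF form. SAP 4.2.7.4 summarises duration, steroid use and hospital contact per exacerbation, which fits that form. Nothing describes deriving events from medication or emergency-visit records. The 7-day deduction in the sensitivity analysis also suggests that its authors had the merging rule in mind. All of this stands as a reason why the practical effect may be nil. It does not remove the conflict: the sentence is worded as the operative rule, and nothing in SAP 3.3.2 limits the count to 5.2.2 events.

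A reader might go further and infer that a one-step OCS increase, such as restarting 2.5 mg from 0 mg, would be counted as an exacerbation. The documents do not support that. The therapy reasons in SAP 3.2.1 separate asthma worsening from a per-protocol exacerbation, and SAP 3.2.2 separates a burst from an increase in the maintenance dose. Read with those sections, a course of systemic steroids does not naturally include a maintenance step.

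On Appendix K, the substudy has its own SAP or addendum, which was not available and may harmonise the definitions. The comparison is also descriptive and already limited: no sponsor-supplied benralizumab, free changes of regimen, and retrospective collection. The mismatch is therefore conditional, but nothing in the documents at hand resolves it.

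Protocol 5.1.2.1 also mentions emergency room admission without spelling out a steroid condition. That passage governs when titration is interrupted, not how the rate is counted, so it does not license the SAP rule.

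**Conclusion.** The inconsistency is real and undeclared. As written, SAP 3.3.2 would admit bursts shorter than 3 days and emergency or urgent-care visits without qualifying steroids into the annualised rate. It would also admit such emergency room visits into the hospitalisation or emergency room rate. Any excess raises the main-study rate relative to a substudy rate based on 5.2.2.

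The documents do not fix the size. It is zero if only investigator-recorded 5.2.2 events are counted. Under the assumptions above (6 to 60 extra events, 36 to 52 weeks, no withdrawals), the addition is about 0.010 to 0.145 per patient-year. The duration range is itself optimistic, because the synopsis figures presuppose complete withdrawal with no exacerbation and no adrenal risk. Longer follow-up would shrink the effect per event, and withdrawals would enlarge it.

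A reader might infer that the reported rate is known to be inflated, or that the primary endpoints are affected. Neither follows. The first depends on how the count is programmed, and the rule in SAP 3.3.2 serves the safety rates, not the OCS-reduction endpoints.

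**What to change.** Replace the definition sentence in SAP 3.3.2 with: *An asthma exacerbation is an event that satisfies CSP section 5.2.2 and is entered on the exacerbation eCRF. An event starting no more than 7 days after the final systemic steroid dose for an earlier exacerbation is merged with that earlier event.* Apply this to both annualised rates, to the counts in SAP 4.2.7.4, and to the main-study rate used in the Appendix K comparison. If the broader count is wanted, keep it as a labelled sensitivity analysis and list it in SAP section 6.

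The cost is one SAP paragraph, plus one line in section 6 if the broader count is kept. No new data are needed, because Protocol 5.2.2 already requires the eCRF record. The downside is that any tables already produced under the broader rule, including any from the first database lock, would have to be re-run.
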